### **11.6.2 Serious Adverse Event Reporting**

In the event of any SAE reported or observed during the study, whether or not attributable to the study drug, site personnel will report it immediately (within 24 hours of becoming aware of the SAE) by telephone, fax, or email to the Sponsor, Allakos, Inc.

Serious adverse events must be reported to:

[REDACTED], MD, PhD

[REDACTED]

Phone: [REDACTED]

Fax: [REDACTED]

Email: [contact]

Serious adverse event report forms will be provided to the investigational site to assist in collecting, organizing, and reporting SAEs and follow-up information will be completed within 24 hours. SAEs should also be recorded in EDC on the AE eCRF and designated as “serious.”

The site will notify the Institutional Review Board (IRB)/ local authorities according to its guidelines. All SAE report forms will be completed within 24 hours. All efforts will be made to obtain accurate and complete medical records for the SAE.

The patient’s condition will be followed by the Investigator or designated Sub-investigator until resolution of the condition or a return to baseline levels. If additional visits are required, the patient will be asked to return to the study site for further follow-up. If condition is still ongoing at the time the patient exits the study, every effort will be made to continue to follow up with the patient for a reasonable period of time, or until there is a return to baseline or stabilization of the condition. As additional information becomes available, such as hospital discharge notes and patient medical records, the Investigator will be notified and provided with all relevant information.

All SAEs that have not resolved by the end of the study, or that have not resolved upon discontinuation of the patient’s participation in the study, must be followed until any of the following occurs:

- The event resolves
- The event stabilizes
- The event returns to baseline, if a baseline value is available
- The event can be attributed to agents other than the investigational product or to factors unrelated to study conduct
- It becomes unlikely that any additional information can be obtained (patient or health care practitioner refusal to provide additional information, lost to follow-up after demonstration of due diligence with follow-up efforts)

### **11.6.3 Pregnancy Reporting**

Female subjects must be instructed to discontinue all study drugs and inform the Investigator immediately if they become pregnant during the study.

The Investigator must report any pregnancy to Allakos, Inc. within 24 hours of becoming aware of it using the provided pregnancy reporting forms. The patient must be immediately discontinued from study drug. An uncomplicated pregnancy will not be considered an AE or SAE, but all pregnancies will be followed through term.

Pregnancies are captured if they occur in female subjects or in the sexual partners of male subjects from the time the patient is first exposed to the study drug until 120 days after last dose received.

Any congenital abnormalities noted at birth in the offspring of a patient who received study drug will be reported as an SAE. The outcome of any pregnancy and the presence or absence of any congenital abnormality will be recorded in the source documentation and reported to the Medical Monitor and Sponsor.

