Centers/Countries	Approximately 4 study centers in the USA and Germany. Only the sites in Germany will participate in the extension study.
Number of Subjects	
N (total) = Approximately 48 subjects with chronic urticaria
 
This will include the following cohorts:
 
 
• Approximately 12 subjects with Cholinergic urticaria (CholU)
 
• Approximately 12 subjects with Urticaria factitia (UF)
 
• Approximately 12 XOLAIR® (omalizumab) naïve subjects with Chronic spontaneous urticaria (CSU)
 
• Approximately 12 subjects with Chronic spontaneous urticaria (CSU) who did not achieve an adequate response on XOLAIR® (omalizumab) in the opinion of the Investigator
 
 
The extended dosing will be applicable only to the subjects in the CholU, UF, and CSU-XOLAIR® (omalizumab) failure cohorts.

Rationale for Sample Size	The planned sample size of approximately 48 subjects is based on common practice in early phase, proof-of-concept studies.
Duration of Patient Participation and Duration of Study	
The total study duration for each patient will be approximately 32 weeks. This includes:
 
 
• A screening period of 4 weeks prior to study drug administration
 
• Administration of study drug at Day 1, Day 29, Day 57, Day 85, Day 113, and Day 141
 
• Follow-up through Day 197 (8 weeks post last dose)
 

Duration of Patient Participation and Study cont.	Subjects who elect to receive optional extended dosing with up to 12 additional doses of AK002 will participate for up to an additional 12 months (see Appendix 2 ).

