#### **7.2.1 Inclusion Criteria**

- 1) Adults ( $\geq 18$  and  $\leq 85$  years old)
- 2) Body weight  $< 125$  Kg
- 3) Informed consent signed and dated
- 4) Able to read, understand, and willing to sign the informed consent form and comply with study procedures
- 5) Diagnosis of CU for at least three months, refractory to antihistamine treatment in single or 4-fold dosage
- 6) Willing, committed, and able to return for all clinic visits and complete all study-related procedures, including willingness to have IV infusion of study drug administered by a qualified person
- 7) Females of childbearing potential must have a negative pregnancy test at Baseline. Female subjects must be willing to use highly effective contraception (Pearl-4 Index  $< 1$ ) or abstain from sexual activity from Screening until the end of the study, or for 120 days following the last dose of study drug, whichever is longer. A woman will be considered not of childbearing potential if she is post-menopausal for greater than two years (FSH  $> 40$  mL) or surgically sterile (bilateral tubal ligation, bilateral oophorectomy, or hysterectomy).

Male patients with female partners of childbearing potential must agree to use a highly effective method of contraception from Screening until the end of the study or for 120 days following the last dose of study drug, whichever is longer. All fertile men with female partners of childbearing potential should be instructed to contact the Investigator immediately if they suspect their partner might be pregnant (e.g., missed or late menstrual period) at any time during study participation.

- 8) No participation in other clinical trials 4 weeks before participation in this study
- 9) Uncontrolled CU (UCT <12) at the time of enrollment
- 10) For extended dosing, subjects must have a baseline (Day 1) UCT of  $\leq 5$  and a week 22 (Day 155) UCT of  $\geq 12$  (Complete Response). They must have a UCT of  $\leq 5$  between Day 155 and Day 309 (i.e., within 6 months from last dose).

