### **9.2 Definition of Study Completion**

A patient who completes visits through the end of the Follow-Up visit at Week 28 will be recorded as having completed the study.

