## **10. Visit Schedule and Assessments**

[Table 3](#) shows the schedule of assessments by study visit. Subjects should be seen for all visits on the designated day or as close to it as possible.

Subjects discontinuing the study drug before completing the 12-week treatment period, and those who prematurely withdraw from the study for any reason, should be scheduled for an early termination visit as soon as possible, at which time all of the assessments listed for the final visit will be performed.

Subjects who discontinue AK002 treatment also should return for the final assessments. If they refuse to return or are unable to do so, every effort should be made to contact them or a knowledgeable informant by telephone to determine the use of rescue medication and to complete the [REDACTED].

At a minimum, they will be contacted for safety evaluations during the 28 days following the last dose of AK002, including the final contact at the 28-day point. Documentation of attempts to contact the patient should be recorded in the patient record.

All data obtained from the assessments listed in Table 3 and described in detail in the protocol must be supported in the patient's source documentation.

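### The protocol captures pregnancies to 120 days after the last dose, but scheduled contact ends at 56 days (28 for many who stop early), so later pregnancies depend on volunteered reports

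*Protocol*

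**What the plan says.** **Capture window.** Section 11.6.3 of the protocol captures pregnancies in female subjects and in sexual partners of male subjects "from the time the patient is first exposed to the study drug until 120 days after last dose received". Inclusion criterion 7 (section 7.2.1, repeated as criterion 9 in Appendix 2) requires contraception to the end of the study or for 120 days after the last dose, whichever is longer.

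**Scheduled contact.** The synopsis plans "Administration of study drug at Day 1, Day 29, Day 57, Day 85, Day 113, and Day 141", with follow-up to Day 197. Section 9.2 fixes completion there: "A patient who completes visits through the end of the Follow-Up visit at Week 28 will be recorded as having completed the study". Table 3 labels that visit as end of study and places the last urine pregnancy test at it. Sections 9.1 and 9.3 bring subjects who stop early back at 28 (±2) days after the last dose. For subjects who stop AK002 and do not return for the final assessments, section 10 sets a floor: "they will be contacted for safety evaluations during the 28 days following the last dose of AK002, including the final contact at the 28-day point". In the extension, the last dose is on Extended Day 309 and the final visit on Extended Day 365, or 28 (±3) days after the last dose at early termination.

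**Reporting instructions.** Women are to be told to "inform the Investigator immediately if they become pregnant during the study" (section 11.6.3). Men are to contact the investigator "if they suspect their partner might be pregnant (e.g., missed or late menstrual period) at any time during study participation" (section 7.2.1). Section 10.5.11 speaks of pregnancies in a patient on study drug. The investigator must report any pregnancy to the sponsor within 24 hours of becoming aware of it; no end date is attached to that duty.

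**The concern.** The protocol names a period in which pregnancies count, but its visits, tests and calls stop well inside that period, and the wording of the instructions does not clearly carry subjects to its end. A pregnancy that begins, or is first recognised, after the last visit enters the record only if the subject chooses to tell the site.

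What is at stake is safety reporting. Section 11.6.3 requires every pregnancy to be followed through term and treats a congenital abnormality as a serious adverse event. When very few pregnancies are expected, one unreported case can be the whole of the evidence. A study report stating that pregnancies were captured to 120 days would have no scheduled contact behind it for the later part of the window.

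**Working it through.** This is calendar arithmetic.

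**Inputs:** last dose Day 141 (±2) and final visit Day 197 (±2), from Table 3; post-dose window 120 days, section 11.6.3; early-stopping return 28 (±2) days, sections 9.1 and 9.3; extension last dose Extended Day 309 (±2) and final visit Extended Day 365 (±3), or early termination at 28 (±3) days, Table 9.

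**The plan's own figure.** 197 − 141 = 56 days = 8 weeks, which agrees with the synopsis. For the extension, 365 − 309 = 56 days.

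**Gap.** Gap = 120 − follow-up; share = gap / 120.

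| Group | Follow-up (days) | Gap (days) | Share of 120 | With visit windows |
|---|---|---|---|---|
| Main study, completers | 56 | 64 | 53.3% | follow-up 52–60, gap 60–68, 50.0–56.7% |
| Main study, last seen at 28 days | 28 | 92 | 76.7% | follow-up 26–30, gap 90–94, 75.0–78.3% |
| Extension, completers | 56 | 64 | 53.3% | follow-up 51–61, gap 59–69, 49.2–57.5% |
| Extension, early termination | 28 | 92 | 76.7% | follow-up 25–31, gap 89–95, 74.2–79.2% |

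**End of the window.** 141 + 120 = Day 261 for main-study completers, 64 days after the Day 197 visit.

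**Other denominator.** The capture sentence starts at first exposure. From Day 1 to Day 261 is 260 days, so the completer gap is 64 / 260 = 24.6% of the whole window.

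**Expected events.** Take as an assumption the contraceptive failure rate implied by inclusion criterion 7 (Pearl Index below 1, so at most 0.01 per person-year). Overcount by treating all 48 subjects as at risk:
- 64-day gap: 48 × 64 / 365.25 × 0.01 = 0.08 pregnancies.
- 92-day gap for everyone: 48 × 92 / 365.25 × 0.01 = 0.12 pregnancies.
- With a failure rate ten times higher: about 0.8 and 1.2.

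**A related mismatch.** SAP section 3.9.6 lists urine pregnancy tests at Visits 2 to 7 only, whereas Table 3 of the protocol and Table 1 of the SAP run them through Visit 10.

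**The case against.** The best counter-argument is that the capture sentence defines which pregnancies are reportable once known and does not promise active surveillance, so visits need not span the window. That reading is possible. A reader might infer that the protocol claims complete capture; the text does not say so.

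A reader might also infer that the later part of the window is wholly unobserved, or that no instruction of any kind covers it. The documents do not support that either:
- The investigator's 24-hour duty has no end date.
- Subjects carry a study card with a 24-hour number (section 11.6.1).
- The 120-day contraception requirement tells them that the period matters.
- For women, the reporting period could be read as running to the end of trial, which section 10.6 defines as last patient, last visit. For early enrollees that may lie beyond their own 120 days. It would not for the last to finish, and it does not help the instruction to men.
- Consent pages were not available and may contain a further instruction.

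Two limits on the size also stand. The 28-day contact is not universal: some early terminators are seen sooner and those who leave during follow-up are seen later. Subjects who enter the extension have later contact, although they meet the same gap at its end.

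What remains is that none of these routes makes the site aware of a pregnancy after the last visit unless the subject volunteers it.

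**Conclusion.** The mismatch holds. Of the 120 post-dose days, 64 (53%) have no scheduled contact for completers and 92 (77%) for those last seen at 28 days, with the same pattern in the extension. Over half is a statement about the post-dose window at nominal visit days; it falls to 50% (main study) or 49% (extension) at the extreme of the visit windows, and to about 25% for main-study completers when counted from first exposure.

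The exact description is that this period lacks scheduled contact, and that the reporting instruction is too short for men and ambiguous for women. The conclusion rests on the protocol text alone. The expected number of pregnancies in the gap is small, so the consequence is for the completeness of safety reporting. No endpoint or efficacy analysis is affected. It is worth correcting because the correction is cheap.

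**What to change.** 1. Reconcile sections 11.6.3, 10.5.11 and 7.2.1 (criterion 7) with Appendix 2 (criterion 9), so that the reporting instructions to female and male subjects run for the same 120 days that the protocol already sets for capture. Check the consent form against the result.
2. Support the window with one documented telephone contact at its end, asking about pregnancy, for women of childbearing potential and men with such partners. That is about Day 261 for main-study completers, and 120 days after the actual last dose for early terminators and extension subjects. The existing 24-hour rule then applies to anything reported.
3. Keep this contact outside the Week 28 database lock.
4. Reconcile SAP section 3.9.6 with the two schedule tables on the visits with urine pregnancy tests.

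The 120 days are the sponsor's own figure, and nothing here changes contraception, testing or treatment rules. The cost is amendment wording and one call, 64 days (about 9 weeks) after the last visit for completers and 92 days after the last contact for those last seen at 28 days, to a subset of about 48 subjects. There is no added visit or procedure.

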### **11.7 Anaphylaxis**

Signs or symptoms of anaphylaxis will be carefully monitored and treated according to standard of care. In addition, as part of the anaphylaxis assessment, a sample of blood should be obtained for plasma histamine and tryptase level within 1 hour of the onset of the symptoms. Emergency crash cart equipment and medications, including multiple doses of epinephrine, pressors, and bronchodilators, will be available at all times during the conduct of the study. To define anaphylactic reactions in a consistent and objective manner, all AEs of suspected anaphylaxis will be evaluated using the criteria specified in [Appendix 1](#).

## 12. Data Review and Database Management

### 12.1 Site Monitoring

The Investigator must maintain source documents for each patient in the study, consisting of case and visit notes (hospital or clinic medical records) containing demographic and medical information, laboratory data, electrocardiograms, and the results of any other tests or assessments. All information on eCRFs must be traceable to these source documents in the patient's file. Data not requiring a separate written record will be defined before study start and will be recorded directly on the eCRFs, which will be documented as being the source data. The Investigator must also keep the original informed consent form signed by the patient (a signed copy is given to the patient).

The Investigator must give the monitor access to all relevant source documents to confirm their consistency with the CRF entries. Monitoring standards require full verification for the presence of informed consent, adherence to the inclusion/exclusion criteria, documentation of SAEs, and the recording of data that will be used for all primary and safety variables. Additional checks of the consistency of the source data with the CRFs are performed according to the study-specific monitoring plan. No information in source documents about the identity of the subjects will be disclosed.

### 12.2 General Safety Monitoring

The Investigators and Medical Monitor will review data relating to safety and to conduct of the study.

The trial must be discontinued prematurely in the event of any of the following:

- A life-threatening AE that is possibly or probably related to treatment
- A fatal AE that is possibly or probably related to treatment

- New information leading to unfavorable risk-benefit judgment of the study drug, e.g., occurrence of significant previously unknown adverse reactions or unexpectedly high intensity or incidence of known adverse reactions, or other unfavorable safety findings
- >50% of subjects at any time have been withdrawn due to drug-related AEs, including those related to abnormal laboratory results, or other safety findings
- Sponsor's decision that continuation of the trial is unjustifiable for medical or ethical reasons
- Poor enrollment of subjects making completion of the trial within an acceptable time frame unlikely
- Discontinuation of development of the Sponsor's study drug

Health Authorities and IECs will be informed about the discontinuation of the trial in accordance with applicable regulations. The trial may be terminated or suspended upon request of Health Authorities.

### **13. Data Analysis**

This section outlines the statistical methods to be used for the analysis of the data from the study. A separate Statistical Analysis Plan (SAP), which will be completed and signed off prior to data base lock.

When the SAP differs from analyses described in the protocol, the SAP will take precedence.

Continuous variables will be summarized using number of non-missing observations, mean, standard deviation (SD), median, minimum, and maximum; categorical variables will be summarized using the frequency count and the percentage of subjects in each category.

Baseline for data analysis is defined as the last assessment prior to the first infusion of the study drug.

The primary summaries will be based on individual cohorts and the data from all 3 cohorts combined, wherever possible.

#### **13.1 Populations for Analysis**

##### **13.1.1 MITT Population**

The modified intent-to-treat (MITT) population will consist of all subjects who are enrolled, have received at least one dose of study drug and have at least one post-baseline assessment of the primary efficacy variable UCT.

### **13.1.2 Safety Population**

The safety population will consist of all subjects who are enrolled, have received at least one dose of study drug.

### **13.1.3 Per-Protocol Population**

The per-protocol (PP) population will consist of all subjects from the MITT-population for whom no major protocol violations adversely affecting the data interpretation are reported.

## **13.2 Disposition of Subjects**

The number of subjects who signed the informed consent, received a dose of study drug, completed, or discontinued from the study and the reason for study discontinuation will be tabulated.

## **13.3 Protocol Deviations**

Major protocol deviations will be summarized. Subjects with major protocol deviations affecting an efficacy evaluation will be excluded from the PP population.

## **13.4 Patient Demographics/Other Baseline Characteristics**

Descriptive statistics of subject characteristics and baseline values will be presented for all populations (total and by cohort).

## **13.5 Treatments (Study Drug, Concomitant Therapies, Compliance)**

Exposure to study drug will be summarized descriptively. The use of rescue medication is part of the efficacy assessment and will be reported there. Other concomitant therapy used both prior to and after start of study drug administration will be summarized. The WHO Drug Dictionary will be used for coding of medications.

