#### 4.2 Secondary Objectives

The effect of AK002 on urticaria symptoms, QOL, provocation testing, and histological criteria

The efficacy, safety and pharmacodynamics of AK002 in CU subjects will be assessed through the following evaluations:

- 1) Safety and tolerability (adverse events, laboratory safety tests, etc.)
- 2) Disease activity scores (UAS7, [REDACTED])
- 3) [REDACTED]
- 4) Number of symptom-free days
- 5) Use of rescue medication (up to 3 sgAH tablets/day)
- 6) Effects on [REDACTED]
- 7) Number of [REDACTED]
- 8) [REDACTED]
- 9) Changes in trigger thresholds (in CINDU, including CholU)
- 10) Rate of [REDACTED] (UCT, [REDACTED]  
[REDACTED])
- 11) Serum levels of potential biomarkers of disease activity and treatment responses
- 12) Rates of relapse and sustained response (during post-treatment follow-up period)

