### 5.2 Other Endpoints

- 1) Safety of subjects treated with AK002: This includes physical examination, routine safety laboratory assessments, vital signs, electrocardiogram (ECG), urine safety, and adverse event reporting (Visits 2–10)
- 2) Change in disease activity as assessed by UAS7 and/or [REDACTED] (from Baseline to Visits 3, 5, 8, and 10)
- 3) Change in number of symptom-free days per week (patient diary-based CSU score; wheals, flares, itch, avoidance behavior) from Baseline to Visits 3, 5, 8, and 10
- 4) Change in [REDACTED] assessed by [REDACTED] from Baseline to Visits 3, 5, 8, and 10
- 5) Change in number of intake of rescue medication from Baseline to Visits 3, 5, 8, and 10
- 6) In case of [REDACTED], change in [REDACTED] from Visit 2 to Visit 3, 5, 8, and 10, as assessed by [REDACTED]
- 7) Change in number of [REDACTED] from Baseline to Visits 3, 5, 8, and 10
- 8) Change in [REDACTED] from Baseline to Visits 3, 5, 8, and 10
- 9) Changes in trigger threshold from Baseline to Visits 2, 3, 5, 8, and 10, as assessed by Pulse Controlled Ergometry Test (PCE) and FricTest®, as applicable
- 10) Rates of complete response, partial response, and non-response based on UCT, [REDACTED], trigger thresholds (where applicable), and QoL from Baseline to Visits 3, 5, 8, and 10
- 11) Serum levels at baseline and change from Baseline to Visits 3, 5, 8, and 10 of serum levels of potential biomarkers in AK002-treated subjects (e.g., tryptase, eosinophils, total IgE, basophils, eosinophil cationic protein)
- 12) Rates of AK002-treated subjects with relapse, rebound, sustained treatment effects at Visit 7

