## 6. Investigational Plan

### 6.1 Study Design

The study comprises a screening period of 4 weeks, with daily oral intake of standard-dose (once daily) second-generation AH (standard of care, with on-demand intake of up to 3 additional AH tablets per day). The treatment period comprises a daily oral intake of standard-dose second-generation AH and AK002 administered by IV infusion at Days 1, 29, 57, 85, 113, and 141.

Subjects will be followed for an additional 8 weeks, and at Weeks 22, 24, and 28 the primary and secondary objectives will be evaluated.

It is expected that approximately 48 subjects will be enrolled and assigned to 3 cohorts:

- Approximately 12 subjects with Cholinergic Urticaria (CholU)
- Approximately 12 subjects with Urticaria Factitia (UF)
- Approximately 12 XOLAIR® (omalizumab) naïve subjects with Chronic spontaneous urticaria (CSU)
- Approximately 12 subjects with Chronic spontaneous urticaria (CSU) who did not achieve an adequate response to XOLAIR® (omalizumab) in the opinion of the Investigator

The open-label design facilitates the assessment of efficacy, as well as safety in the cohort.

Table 1 shows the study outline and Table 3 shows the schedule of assessments.

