### **6.1.2 Treatment Period**

During the Treatment Period, all eligible subjects will receive AK002 by IV infusion every 28 days. The first dose will be administered at the beginning of the treatment period Day 1 (Visit 2) after baseline measurements. At Day 141 ( $\pm 2$  days) (Visit 7), the final dose of AK002 will be given. Throughout the treatment period, subjects must maintain stable doses of their baseline AH dose and treatment regimen and remain on a stable treatment regimen through the end of the study. Patient's use of rescue medication will be monitored and reviewed throughout the treatment period and if necessary adjusted according to the current urticaria guidelines ([Zuberbier, 2014](#)). Subjects are expected to attend all site visits based on the assessment schedule (see [Table 3](#)).

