### **8.2 Concomitant Treatment**

One hour prior to dosing with AK002, subjects will receive pre-treatment oral doses of acetaminophen/paracetamol (1000 mg) and cetirizine (10 mg) for doses 1 and 2. Any premedication for subsequent doses will be based on the Investigator's discretion.

Subjects will be treated with a standard dose of second-generation AH (once per day) or up to a 4-fold dose of second-generation AH (standard of care) with dose and regimen established during Screening. In the event of symptom resolution during the study, the dose and schedule of AH treatment established during screening must be continued throughout the study.

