## **13.7 Analysis of Secondary Objectives**

### **13.7.1 Secondary Efficacy Variables**

The [REDACTED], and weekly number of symptom-free days will be summarized analogous to the primary endpoint, as a mean difference from Baseline (Visit 1) to weeks 4, 8, 12, 16, 20, 22, 24, and 28.

Number and percent of subjects receiving rescue medication will be summarized.

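### On the readable text, two rescue-medication summaries planned in the protocol have no counterpart in the governing SAP, which declares no changes from the protocol

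*Protocol*

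**What the plan says.** The protocol treats rescue medication as an efficacy matter in four places. Use of up to three second-generation antihistamine tablets a day is item 5 of the secondary objectives (4.2). Item 5 of the other endpoints (5.2) is "Change in number of intake of rescue medication from Baseline to Visits 3, 5, 8, and 10". Section 13.5 sets rescue apart from other concomitant therapy: "The use of rescue medication is part of the efficacy assessment and will be reported there". Section 13.7.1 adds: "Number and percent of subjects receiving rescue medication will be summarized".

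The SAP schedules a rescue-medication record at Visits 2 to 10 (Table 1), and all three diary versions ask for it (Appendices B.1.1 to B.1.3). Its secondary endpoints (5.2) and secondary efficacy analyses (7.7.1.3), both fully readable, cover UCT responses and UAS7 only. The readable parts of 5.1 to 5.6 and of 7.7 do not mention rescue medication.

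On precedence, protocol Section 13 says: "When the SAP differs from analyses described in the protocol, the SAP will take precedence". SAP Section 1 likewise says that it supersedes the protocol's methods. SAP 3.7, where changes from the protocol belong, declares none.

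**The concern.** The trial is open-label and single-arm, and its primary endpoint is patient-reported. Background antihistamine is meant to stay fixed: "the dose and schedule of AH treatment established during screening must be continued throughout the study" (Protocol 8.2). Rescue is the part that may move. It is taken on demand, "with on-demand intake of up to 3 additional AH tablets per day" (Protocol 6.1), and during treatment "use of rescue medication will be monitored and reviewed throughout the treatment period and if necessary adjusted" (Protocol 6.1.2).

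A reader of the UCT change will want to know whether rescue intake fell, rose or stayed level over the same period. A UCT gain with falling rescue use and one with rising rescue use mean different things. If the governing plan has no such summary, one listed secondary-objective item goes unanswered. The omission might also pass unremarked in the study report, because SAP Section 1 commits the report to flag departures from the SAP, not from the protocol.

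**Working it through.** The plan gives no figure to reproduce. The check is a comparison of texts, followed by arithmetic on what the nearest SAP tables could show and on precision if the summaries are restored.

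**1. Side by side.**

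| Protocol item | Protocol place | Readable SAP endpoint | Readable SAP efficacy analysis | Declared in SAP 3.7 |
|---|---|---|---|---|
| n (%) of rescue users | 13.7.1 | none | none | no |
| Change in rescue intake, Visits 3, 5, 8, 10 | 5.2 no. 5 | none | none | no |

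**2. Could the missing items sit under redaction?**
- In SAP 5.3, the proportion items (nos. 2 to 4) are limited to CSU subjects. Nos. 6 and 7 are changes in something blacked out.
- In SAP 7.7.2, the percentage items 3 and 4 are CSU-only, item 2 is a cumulative distribution of a total score, and items 1 and 6 concern scores. Item 7, and less plausibly item 5, could hold a change in rescue use.
- No readable stem fits an all-cohort n (%) of users. The change endpoint could be hidden.
- Appendices C and D have no readable entries.
- The protocol leaves rescue medication readable in lists whose neighbouring items are blacked out (4.2, 5.2). That makes a hidden item less likely but does not exclude it.

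**3. Does the SAP's no-change statement keep the protocol analysis alive?** It is weak evidence. Under that statement the SAP defines UCT complete response as a score of at least 12 with a gain of at least 3 (Section 4), where protocol 10.4.2 and 13.6.1 require 16. Even if 13.7.1 stands, its readable rescue text covers n (%) only. For the change endpoint, general rules supply a baseline (Protocol 13; SAP Section 4) and descriptive statistics (Protocol 13; SAP 6.1), and the visits are named. The counting window is missing.

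**4. Permitted range.** For one daily background tablet over 28 days, background is 28 tablets and rescue is 0 to 3 × 28 = 84. The maximum share is 84/(28 + 84) = 84/112 = 75%.

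**5. What nearby SAP tables show.**
- SAP 7.6.1 duration is last dose date minus first plus 1. Over Days 1 to 197 this is 197 − 1 + 1 = 197 days, whether rescue totals 0 or 3 × 197 = 591 tablets.
- SAP 7.6.1 also tabulates subjects by number of doses received. If that covers antihistamine and includes rescue, the count could run from 197 to 197 + 591 = 788. It would still merge rescue with background and show no change over time.
- SAP 7.6.2 counts a subject once per preferred term. If rescue and background share a term (an assumption), a cohort with 0 of 12 rescue users and one with 12 of 12 give the same row.
- SAP 6.1 lists diary data by cohort and subject. This is a listing, not a summary.

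**6. Precision if restored.** Exact (Clopper-Pearson) 95% limits:
- 3/12 (25%): 5.5% to 57.2%; 12/48: 13.6% to 39.6%.
- 6/12 (50%): 21.1% to 78.9%; 24/48: 35.2% to 64.8%.

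Half-width for mean change in tablets/day is t(0.975, n−1) × SD/√n. The documents give no SD, so 0.5, 1.0 and 1.5 are assumed:
- n = 12: 0.32, 0.64, 0.95.
- n = 48: 0.15, 0.29, 0.44.

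**7. A workable window.** The 28 days before a visit match the UCT recall.
- Visits on Days 29, 85, 155 and 197 give Days 1–28, 57–84, 127–154 and 169–196. The smallest gap is Days 155–168, or 14 days.
- With Visit 8 on Day 157 and Visit 10 on Day 195, the windows are 129–156 and 167–194, leaving 10 days.
- With Visit 3 on Day 27, the 28 days before it run from Day −2 to Day 26 (no Day 0 in the SAP's numbering). Two of those days belong to the screening diary, so the window must be cut at Day 1.
- Week 10 (Day 10 × 7 + 1 = 71) gives Days 43–70.

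**The case against.** The best case on the other side has four parts.

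First, what is blacked out is not missing. SAP 5.3 and 7.7.2 contain change items whose content is redacted, and the tables list and shells are unreadable. This stands as a limit: the finding concerns the readable text only.

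Second, the endpoint is less under-specified than it may seem. A reader might infer that it has no baseline or method at all. The documents do not support that, since both define baseline and both prescribe descriptive statistics. Only the window is absent. It does matter for a daily count, because the last assessment before first infusion, applied literally to a diary, could be a single day.

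Third, the information is not lost. Diary data will be listed, and SAP 7.6.1 promises antihistamine compliance and exposure summaries with a tabulation of doses received. A reader might infer that the SAP outputs cannot reveal rescue use; that goes too far. What remains is that neither 7.6.1 nor 7.6.2 separates rescue from background or shows change, and a listing of about 48 subjects' daily entries does not replace the planned summary.

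Fourth, this is an exploratory pilot without hypothesis tests, and the primary UCT analysis does not depend on rescue. That stands and bears on severity. The tablets-per-day metric, the 28-day window and the place within the SAP are suggestions; other reasonable choices would do.

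**Conclusion.** The mismatch is real on the readable text. The protocol plans two rescue-medication items, the readable SAP endpoints and efficacy analyses contain neither, and no change is declared. No readable planned summary shows whether rescue use moved alongside UCT. Confidence is moderate, because redacted items and the unreadable appendices could hold one or both summaries.

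The figure of 84 tablets, or 75% of intake, is the permitted maximum for a subject on one daily background tablet. It is not an estimate of what will happen. The precision figures assume about 12 subjects per cohort, 48 combined, and the stated SDs.

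A reader might infer that the UCT results are biased, or that the sponsor chose to drop an unwelcome analysis. The documents support neither: the direction of any shift in rescue use is unknown, no effect on UCT can be derived, and an oversight is as consistent with the text as a decision. This is a minor to moderate correction that leaves the primary UCT summary as it is.

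**What to change.** Add to the SAP efficacy endpoints (5.2 or 5.3) and analyses (7.7), by cohort and combined:

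1. n (%) of subjects using any rescue medication, by visit.
2. Mean rescue tablets per day and its change from the screening diary at Visits 3, 5, 8 and 10 (Week 10 for Amendment 2.1 subjects), with descriptive statistics and a 95% CI. State the counting window, for example the 28 days before the visit, truncated at Day 1 so that Visit 3 shares no days with baseline.

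Otherwise, declare the removal in SAP 3.7 and justify it. If a redacted item or Appendix C already holds these summaries, only the derivation and window need checking.

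The cost is a little SAP text and programming. No new data are needed: every diary version records rescue as 1, 2 or 3 tablets, and the diary starts at Visit 1. The downsides are imprecise estimates at about 12 subjects per cohort, and UCT results that may look less favourable if rescue use rose.
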